6.3 STUDY INTERVENTION COMPLIANCE

In practices randomized to share the CAPTURE results with the clinician, the goal is to share results with the clinician at the time of the CAPTURE study visit. Providing results at the time of the clinical visit will allow the clinician to act on the CAPTURE results as soon as possible when the participant is in front of

the clinician. Based on the workflow at each of the practices, this may not always be possible.

Sharing of the CAPTURE results with the participant's primary care clinician will be tracked by the study coordinator enrolling patients at sites randomized to receive CAPTURE results. The sharing of CAPTURE results will be recorded on the study eCRF form. The eCRF will collect the timing of when the results were provided to the practitioner - whether the results were provided to the clinician at the time of the enrollment visit prior to the clinician visit with the patient, or were provided at another time.

If results were not shared at the time of the CAPTURE study visit, then the date of sending the CAPTURE results will be recorded on the appropriate eCRF by filling in the date (day/month/year) the exact copy of the CAPTURE Tool were sent to the clinician through a HIPPA-compliant method and placed in the medical record. The goal is to communicate the results to the clinician. The DCC will monitor review all participants' eCRFs to assure that all those enrolled from practices randomized to CAPTURE results have been shared with clinicians.

6.4 CONCOMITANT THERAPY

Practitioners will treat participants using their own clinical judgment. No medications are prohibited. This is not an interventional therapeutic trial.

7 STUDY INTERVENTION DISCONTINUATION AND PARTICIPANT DISCONTINUATION/WITHDRAWAL

7.1 DISCONTINUATION OF STUDY INTERVENTION

In this cluster randomized controlled trial (Aim 3), where practices are the recipients of the intervention and where the interventions are based upon education and access to CAPTURE and PEF results, it is not anticipated that study intervention will be discontinued at the practice level. However, one of the CO-PIs will review safety data, especially SAEs related to baseline spirometry and PEF procedures, to ensure there are no untoward effects of the study on participants.

7.2 PARTICIPANT DISCONTINUATION/WITHDRAWAL FROM THE STUDY

Participants are free to withdraw from participation in Aims 1 and 3 of the study at any time upon request.

Clinician participants in Aim 2 are free to withdraw from participation in the study at any time upon request. If a clinician is no longer working at the participating practice then their involvement in Aim 2 activities will end and no further attempt will be made to include them in the remaining questionnaires or focus groups.

7.3 LOST TO FOLLOW-UP

If a participant selected for longitudinal follow up does not respond to the 12-month questionnaires, coordinators will attempt to contact participants first by the participant's preferred method of communication, either phone or email. At least three attempts will be made. If no response is obtained, the participant's alternate contact method will be attempted three times. Phone calls will be made at different times of the day. If there is no response, a letter will be sent to the participant. If the participant cannot be reached, the alternate contact will be called and/or emailed. If no response is received, a letter will be sent to the alternate contact. If after all of these methods are employed and no

contact with the participant results, the participant will be considered lost to follow-up.

8 STUDY ASSESSMENTS AND PROCEDURES

8.1 BASELINE ASSESSMENTS AND DATA COLLECTION

Efficacy data will be collected by patient-reported outcomes and medical record review.

For Aim 1, CAPTURE, PEF results, acute respiratory event history and spirometry will be considered efficacy assessments. They are collected at the baseline visit.

CAPTURE. Participants will complete the 5-item *self-administered* questionnaire and measurement of Peak Expiratory Flow (PEF).

Peak Expiratory Flow (PEF). PEF using the Vitalograph® AsmaPlan® mechanical PEF meter with SafeTway® disposable mouthpieces (Vitalograph LTD, UK) will be measured for all participants. Ideally, PEF should be prior to the participant's physician appointment. The participant will perform three PEF tests. All three measurements will be recorded.

Spirometry. Before spirometry is performed, participants will be asked if they have taken a medicine which they breathed into their lungs from any puffer or inhaler within the past two hours. If participant answers yes, then spirometry will be performed but considered a post-bronchodilator spirometry test. No further spirometry will be needed. If participant answers no, then pre-bronchodilator spirometry will be performed for measurement of forced vital capacity (FVC), forced expiratory volume in one-second (FEV₁), and calculation of FEV₁/FVC (using EasyOne® Spirometer, ndd Medical Technologies Inc., Andover, MA). Testing will be performed in accordance with established American Thoracic Society/European Thoracic Society (ATS/ERS) standards. Local guidelines to minimize risk of SARS-CoV-2 infection will be adhered to, including a minimum of appropriate PPE and infection control techniques.

A Spirometry post-bronchodilator will only be performed if pre-bronchodilator spirometry FEV₁/FVC is less than 0.70 or FEV₁ is less than 80% predicted. Post-bronchodilator spirometry will be performed within 15 to 20 minutes after inhalation of 2 puffs of albuterol 180 mcg HFA using an AeroChamber Plus* Flow-Vu® spacer with one minute between the first and the second inhalation. A separate AeroChamber or comparable spacer, using a one way valve to minimize infectious risk, will be provided for each participant's testing. A standing order for albuterol administration may be used if necessary.

Spirometry is a valid, reproducible means of documenting the presence and severity of airflow limitation. When properly performed with maximum effort and attention to the details of calibration of the instrument, spirometry maneuvers are among the most reproducible of biomedical measures. In the setting of a highly trained, experienced therapist, a coefficient of variation of 2-3% is not unusual. Spirometry will be performed in a standardized manner in accordance with the ATS guidelines, as described in the manual of procedures (MOP). Spirometry is the timed-based measurement of the amount of air that can be forcefully exhaled from the lungs after a full inspiration. In the forced expiratory vital capacity maneuver, a person inhales as big a breath as possible and then blows it out as fast and as long as possible until no more air can leave the lungs. The volume of air leaving the lungs is recorded continuously throughout the maneuver in order to allow calculation of important measures of lung function.

NHANES prediction equations, which are programmed into the Easy On PC spirometers, will be used to

calculate the predicted lung function levels. These require the input of age, height, and race/ethnicity (White, Black, Hispanic). For people of mixed or unknown race the White prediction equations will be used.

PBRN Research Coordinators will be trained and certified in the performance of spirometry testing. Spirometry will be sent for central review for quality control assurance.

Adjudication of the Presence of Obstruction on Post-Bronchodilator Spirometry

The presence of obstruction is determined by the presence of an FEV₁/FVC ratio less than 0.70 after the administration of a bronchodilator. A bronchodilator will be administered to study subjects whose baseline FEV₁/FVC is less than 0.70 or whose FEV₁ is less than 80% of the predicted value.

If a subject is unable to complete a post-bronchodilator spirometry (refusal, technical error on the part of coordinator, etc.), and the pre-bronchodilator FEV₁/FVC is less than 0.65, the patient will be considered to have COPD for the purpose of follow-up in this study.

Height and weight

Height and weight will be recorded in order to determine appropriate prediction equations for spirometry and possible effect of obesity on spirometry. Height will be recorded and weight will be measured prior to spirometry testing.

Demographic Data Collection

Demographic data including date of birth, gender, ethnicity, race, educational level achieved, daily work schedule, living arrangement and health insurance will be entered into the EDC system.

Contact information including address, phone numbers and email address will be obtained. Alternate contact information will be obtained for two other people, family members not living with the participant or close contacts, who may be knowledgeable about the participant in the event that the participant cannot be contacted for subsequent longitudinal follow-up. Alternate contact information will include name, address, phone numbers and email addresses. All contact information will be stored securely at the clinical site or in a database separate from that developed for the clinical data.

Medical History

Previous medical diagnoses will include comorbidities such as cardiovascular, respiratory and malignant disorders. Influenza vaccination history will also be recorded. This questionnaire will be completed under supervision of the coordinator.

Concomitant Medication Review

Respiratory medications will be recorded at baseline for all participants. This questionnaire will be completed under supervision of the coordinator.

CAPTURE Additional Items Questionnaire

Participants will complete the 13-item *self-administered* questionnaire.

COPD Assessment Test (CAT)

Participants will complete the 8-item *self-administered* questionnaire.

Respiratory symptoms, smoke exposure and exacerbation like events

History of respiratory symptoms and exacerbation like events over the past year as well as smoke exposure (including e-cigarette or equivalent) will be recorded. This questionnaire will be completed

Whenever possible, informed consent, eligibility review, CAPTURE Questionnaire and PEF will be performed prior to the participant's clinic appointment, so that CAPTURE results may be provided to the physician at the time of his/her appointment if the patient is cared for in a clinical center randomized to CAPTURE+ education.

COVID-19 Additional Items Questionnaire

Participants will complete the 18-item *self-administered* questionnaire.

Adverse events

Adverse events related to study procedures will be recorded by the coordinator.

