4. Pre-bronchodilator spirometry will be done for all participants. Post- bronchodilator spirometry will be performed for participants with abnormal spirometry ($FEV_1/FVC < 0.70$ or $FEV_1 < 80\%$ predicted) *If the participant has taken a bronchodilator within a 2-hour window of spirometry the spirometry will be considered post-bronchodilator and a pre-bronchodilator spirometry will not be done.

5. The 12-month assessment consists of patient reported data, collected by the COPD Foundation, and medical record review completed by site coordinators.

6. This will be completed in those that are smoking at V1.

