| Section 11.2 Organizational Structure | 51 | Clarification | Includes 1 representative of the COPD Foundation in the Executive Committee Organization description. | COPD Foundation representatives are part of the Executive Committee currently |
| Section 4.1 Overall Study Design | 9, 10, 21 | New | Deletion of CAT Score \geq 10 and CAPTURE Score \geq 2 and return to CAPTURE+ and abnormal spirometry as longitudinal follow-up criteria | The study team proposes to defer longitudinal follow-up based solely on an isolated, baseline CAT or CAPTURE scores as it is outside the scope of the current CAPTURE program. The study team is also proposing to return to the original scientific approach to follow CAPTURE+ (as defined in the protocol) subjects along with abnormal post-BD spirometry and 5% |

| | | | | |
|--|-----------|-----|---|---|
| | | | | random sample of those subjects that meet neither of these criteria. Those subjects already selected under the current algorithm would still be followed longitudinally (and noted as selected under the initial follow-up selection criteria) and would use data as appropriate. Importantly, the primary care clinician colleagues within the CAPTURE program do not feel there is a safety issue in not following this population as there are no data defining a negative impact of an isolated, elevated CAT score in primary care patients. |
| Section 1.1 Synopsis, Section 4.1 Overall Study Design, Section 8.1 Baseline Assessments and Data Collection | 3, 20, 29 | New | Addition of adjudication of the presence of obstruction on post-bronchodilator spirometry | As the study commenced, several instances of the faulty spirometry software reading incomplete or participant refusal of post-bronchodilator occurred and led to the need for spirometry core to determine review process in these instances and validity of pre-bronchodilator spirometry. The rationale for this is that in other databases where all patients had both pre and post-bronchodilator spirometry, those who had a pre-bronchodilator FEV1/FVC less than 0.65 had a post-bronchodilator FEV1/FVC less than 0.70 more than 95% of the time. |

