| 8.1 Baseline Assessments and Data Collection | 28 | New | Addition of spirometry instructions if participant has taken a medicine they breathed into lungs from puffer or inhaler within two hours of spirometry test | Since study start, one participant reported taking albuterol shortly before the visit. The study clinicians confirmed this scenario would constitute the participant being in a post-bronchodilator state already with no further need to proceed after initial spirometry. The data collection process has been updated to assure these values would be placed in post-bronchodilator data. Coordinators are instructed to ask this question before spirometry should this scenario occur again during the study. |

Protocol Amendment 3.0 - Summary of Changes

| Location | Page Number | Type of Change | Description | Rationale |
|----------------------|-------------|----------------|---|---|
| Cover Page | --- | Administrative | Update Protocol Version to 3.0 and update version date to 24 September 2019 | Amendment version and date updated |
| Cover Page | --- | Administrative | Add NCT # for each AIM | Add all 3 numbers to protocol since each AIM is registered in clinicaltrials.gov |
| Multiple Sections | Multiple | Revision | Number of PBRNs participating in aims 1 and 2 revised to 6 PBRNs throughout protocol. | Additional PBRN added |
| 1.2 Schema Table 1 | 9 | Revision | CAPTURE 12 additional items questionnaire | The CAPTURE 12 item additional questionnaire was renamed. |
| Section 8.1 Baseline | 30 | Clarification | CAPTURE Additional Items Questionnaire administration | Further instruction for administration of CAPTURE Additional Items Questionnaire, |

| Assessments and Data Collection | | | instruction added to Study Assessments. | as described in Section 1.2 Schema table, was added. |
|--|-------------|----------------|--|--|
| Section 11.1.2 Practice Based Research Networks (PBRN) | 48 | Revision | University of Illinois, Chicago added as a participating PBRN. | University of Illinois, Chicago added as an enrolling site in aims 1 and 3. |
| Protocol Amendment 4.0 - Summary of Changes | | | | |
| Location | Page Number | Type of Change | Description | Rationale |
| Protocol Amendment Summary of Changes Table | --- | Administrative | Protocol Amendment 2.0 – Summary of Changes was added to the Summary of Protocol Amendments Table. | Amendment 2.0 – Summary of Changes was added to provide a comprehensive list of changes across all protocol amendments. |

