10.3 Demographic and Baseline Variables

Demographic and baseline variables for patient participants include:

- Age in years at consent
- Sex (Male, Female)
- BMI
- Race (American Indian/Alaska Native, Asian, Native Hawaiian or Other Pacific Islander, Black or African American, White, Unknown or Not Reported)

- Ethnicity (Hispanic/Latino, Non-Hispanic/Latino, Unknown or Not Reported)
- Educational status (Less than High School Graduate, High School Graduate/GED, Vocational/Some College, College Degree, Professional/Graduate Degree, or Not Reported)
- Employment status (Working, Not working, or Not Reported)
- Smoking status (Current, Former, Never, or Not Reported)
- Living arrangement (Alone, Not alone, or Not Reported)
- Insurance provider (Private, Public, None, or Not Reported)
- Baseline FVC
- Baseline FEV₁
- Baseline FEV₁/FVC
- Use of rescue respiratory medication (Yes if participant uses at least one short-acting bronchodilator, No, or Not Reported)
- Use of maintenance respiratory medication (Yes if participant uses at least one of the following: LABA, LAMA or inhaled corticosteroid [ICS]; No; or Not Reported) and type/combination of medications (ICS alone, LABA or LABA alone, LABA combined with ICS, LAMA combined with ICS, LABA combined with LAMA, LABA and LAMA combined with ICS)
- Cardiac morbidity (Yes if participant lists angina, coronary artery disease, heart attack, coronary artery bypass surgery, angioplasty/cardiac stents or congestive heart failure, No, or Not Reported)
- Use of supplemental oxygen (Yes, No, or Not Reported)
- COPD Assessment Test (CAT) Score
- Cohort membership as defined in section 6.1 (Spirometrically Defined COPD, Clinically Significant COPD, Mild COPD, PRISM, SNO, No COPD by Spirometry).

Practice-level baseline covariates include:

- Location (Rural, Non-rural)
- Type of practice (Federally Qualified Health Care Center
 - Part of large health system, ACO or similar (not affiliated with a medical school),
 - Part of academic medical center/health system, Independent practice, Other)
- Presence of a residency program (Yes, No)
- Practice size as defined as the total number of primary care MD/DOs and NP/PAs
- Ability to perform in-house spirometry (Yes, No).

The primary study demographic and baseline variables table will have columns for CAPTURE positive, CAPTURE negative, and overall study populations. A separate demographics table will be constructed with columns depicting spirometrically defined COPD populations.

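### Protocol 8.1 files spirometry after any inhaler as post-bronchodilator, while the schedule footnotes do so only after a bronchodilator; some participants could be classified on an unbronchodilated test

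*Protocol*

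**What the plan says.** Protocol 8.1 (Spirometry) has the coordinator ask whether the participant has taken "a medicine which they breathed into their lungs from any puffer or inhaler within the past two hours". If so, "then spirometry will be performed but considered a post-bronchodilator spirometry test. No further spirometry will be needed". The question does not ask which drug was inhaled.

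Footnote 4 of the Protocol's Schedule of Activities (1.3) is narrower: "If the participant has taken a bronchodilator within a 2-hour window of spirometry the spirometry will be considered post-bronchodilator". Footnote 4 of the SAP's schedule (7.5) says the same.

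The adjudication paragraph in Protocol 8.1, repeated in SAP 7.6, bases obstruction on a "ratio less than 0.70 after the administration of a bronchodilator". Where no post-bronchodilator test could be completed, a stricter cut-off applies to the pre-bronchodilator value: if the ratio "is less than 0.65, the patient will be considered to have COPD for the purpose of follow-up in this study". The amendment history gives the reason: in other databases, "those who had a pre-bronchodilator FEV1/FVC less than 0.65 had a post-bronchodilator FEV1/FVC less than 0.70 more than 95% of the time".

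Users of non-bronchodilator inhalers are expected. Neither asthma nor maintenance inhalers are exclusions in Protocol 5.2, and SAP 10.3 has a baseline item "type/combination of medications (ICS alone", with other classes following.

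**The concern.** The two triggers send the same person down different paths. Take someone who used only an inhaled corticosteroid an hour before the visit. Under footnote 4, an abnormal first test leads to albuterol and a true post-bronchodilator test. Under 8.1, that first test is itself filed as post-bronchodilator and nothing follows.

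The post-bronchodilator ratio is the core of the Aim 1 reference standard. It also defines the spirometric, clinically significant and mild COPD cohorts in Aim 3, and PRISm uses a post-bronchodilator FEV1. An unbronchodilated value under that label is judged against a limit that the plan does not otherwise accept for such a value.

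**Working it through.** The plan states no figure on this point, so the check is mainly a comparison of texts. Arithmetic is used only for scale.

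**1. The statements side by side**

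| Place | Trigger | Consequence |
|---|---|---|
| Protocol 8.1, Spirometry | Any inhaled medicine in the two hours before | Single test filed as post-bronchodilator; no albuterol step |
| Protocol 1.3 and SAP 7.5, footnote 4 | A bronchodilator in the same window | Single test filed as post-bronchodilator |
| Protocol 8.1 and SAP 7.6, adjudication | None | Obstruction is judged after a bronchodilator has been given |

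**2. Who falls in the gap.** All four conditions must hold:
- a non-bronchodilator inhaler was used within two hours;
- no bronchodilator was taken in that window;
- the coordinator applied 8.1 and not the footnote;
- the first test showed a ratio below 0.70 or FEV1 below 80% predicted.

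Without the last condition, neither wording leads to a further test.

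**3. What the label changes.** For tests already done there is no later test to use, so the comparison is with the plan's own rules for a missing post-bronchodilator test.

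| Unbronchodilated result | Filed as post-bronchodilator | Treated as no post-bronchodilator test |
|---|---|---|
| Ratio 0.65 to <0.70 | Spirometric COPD | COPD rule not met (needs <0.65) |
| Ratio ≥0.70, FEV1 <80% predicted | PRISm | PRISm undetermined (SAP 6.1) |

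For the Aim 1 primary analysis, Protocol 9.2 requires the post-bronchodilator ratio plus either FEV1 below 60% predicted or an exacerbation-like event in the previous year. A mislabelled participant with neither feature is not a case. Protocol 9.2 states no 0.65 fallback, so on this route any unbronchodilated ratio below 0.70 filed as post-bronchodilator could supply the spirometric part.

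The Aim 3 primary population is defined by CAPTURE+ status (SAP 11.1) and does not depend on spirometry.

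**4. Number affected.** The documents do not give it. The rates here are assumptions.
- Assume 0.2%, 0.5% or 1% of 5,000 participants meet the first three conditions: 10, 25 or 50.
- Assume 20% of these have a ratio of 0.65 to 0.70: 2, 5 or 10.
- Against the interim rate in SAP 13.1 (about 2 spirometric COPD patients per practice × 100 practices = 200): 1%, 2.5% or 5%.
- Against the planning figures (300–800 clinically significant cases in Protocol 9.1.1.1 and, by the assumption in Table 9-3, about as many others, so 600–1,600): from 2/1,600 = 0.1% to 10/600 = 1.7%.

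**5. Sensitivity.** The half-width formula 1.96 × √[p(1−p)/n] reproduces the plan: at p = 0.90 it gives 2.63 points for n = 500 (stated ±2.6%) and 0.93 for n = 4,000 (stated ±0.9%). It gives 3.39 for 300 cases and 2.08 for 800.

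If k false cases join n true cases at a true sensitivity of 90%, the shift is (0.9n + qk)/(n + k) − 0.9, where q is the share of false cases that are CAPTURE+. In percentage points:

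| k (assumed) | n = 300, q = 0 | n = 300, q = 1 | n = 800, q = 0 | n = 800, q = 1 |
|---|---|---|---|---|
| 1 | −0.30 | +0.03 | −0.11 | +0.01 |
| 5 | −1.48 | +0.16 | −0.56 | +0.06 |
| 10 | −2.90 | +0.32 | −1.11 | +0.12 |
| 25 | −6.92 | +0.77 | −2.73 | +0.30 |

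For example, with k = 10 and n = 300, 270/300 becomes 280/310 = 90.3% or 270/310 = 87.1%. These are outer limits, because q will lie between 0 and 1.

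**The case against.** The strongest reply is that the gap is narrow and may already be closed in practice. The manual of procedures, which is not among these documents, may ask about bronchodilators specifically. The adjudication paragraph in 8.1 itself calls for a bronchodilator when the first test is abnormal. Spirometry goes to central review, and the Spirometry Core (Protocol 11.1.3) checks bronchodilator procedures and adjudicates tests. Respiratory medicines are recorded at baseline. The amendment history traces the rule to a case where "one participant reported taking albuterol shortly before the visit", which both wordings treat alike. All this supports a small number. It does not remove the contradiction, because none of these safeguards is written as a correction for a non-bronchodilator inhaler.

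Three stronger readings are tempting and are not supported.
- A reader might infer that reversible obstruction, mostly asthma, enters as true positives and raises sensitivity. The documents do not say how such participants score on CAPTURE, and a case also needs FEV1 below 60% or an event. The largest rise in the table is under 0.8 points, and a fall is equally open.
- A reader might infer that the 60% limit is also a post-bronchodilator limit. The definitions attach that term to the ratio and to the 80% limit for PRISm, not to the 60% limit.
- A reader might infer that everyone on a non-bronchodilator inhaler is misclassified. Only those meeting all four conditions above are exposed.

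**Conclusion.** The inconsistency is real and stands in the current text of both documents. Followed as written, 8.1 lets an unbronchodilated ratio of 0.65 to 0.70 count as COPD and turns undetermined PRISm status into definite PRISm.

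The consequence depends on coordinators having used the 8.1 wording. It is confined to Aim 1 and the spirometry-defined Aim 3 secondary cohorts. The illustrative share of spirometric COPD, 0.1% to 5% across both denominators, rests on assumed rates and should not be read as an estimate. No change to a primary result is shown. The point merits action because the label feeds a reference standard and the check is cheap.

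**What to change.** Reconcile Protocol 8.1 with footnote 4 in Protocol 1.3 and SAP 7.5. Which trigger applies at the visit is for the investigators to settle. Rewording alone comes too late for most data: SAP 9.5 reports that by 21 March 2023 the sites with all follow-up collected held about 84% of the patients selected for follow-up.

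Before analysis:
- Flag every test filed as post-bronchodilator that has no pre-bronchodilator test.
- Compare each with the respiratory medicines recorded at baseline.
- Where no bronchodilator-containing inhaler is recorded, treat the post-bronchodilator test as missing and apply the existing rules, or at least do so in a sensitivity analysis. For Aim 1, state how these participants are handled, since Protocol 9.2 gives no fallback.
- Report the number flagged and the number reclassified.

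The cost is one derived variable from data already collected. The downside is that a few participants move to the missing-test rules. The check also cannot settle participants who have both kinds of inhaler, because the plan does not describe recording which one was used in the window; they should be counted separately.
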